## Objectives

- Primary Objectives
  - Validate patient tolerability of needle-free delivery of intralesional triamcinolone using patient-reported outcome measures.
- Secondary Objectives
  - Validate efficacy of needle-free delivery of intralesional triamcinolone for pediatric alopecia areata.
  - Assess the impact of needle-free delivery of intralesional triamcinolone on quality of life for pediatric alopecia areata.

## Background

Alopecia areata (AA) is a significant medical condition that causes emotional and psychosocial distress as well as reductions in quality of life, especially in the pediatric population [Aldhouse et al 2020; Mostaghimi 2021; Christensen et al 2017]. When limited and patchy, an estimated 80% of those affected will see spontaneous recovery; however, this disease is characterized by frequent remittances and relapses and may progress to more severe disease – alopecia totalis or alopecia universalis (Ito 2012; Barton 2021). Currently, there are no Food and Drug Administration- (FDA) approved treatments for pediatric alopecia areata, and there is a paucity of well-designed, randomized-controlled clinical trials (Meah et al 2020; Barton et al. 2021). Current recommendations, however, support the use of intralesional triamcinolone acetonide (ILTA) in adults (Meah et al 2020, Yee et al 2019), and pediatric patients (Barton et al. 2021; Fernando et al. 2020; Wang et al. 2012).

The use of ILTA in the pediatric population is often limited due to fear of injections and pain [Hordinsky 2015]. A 2002 chart review by Tan et al. demonstrated >50% improvement in 65% of pediatric patients at 12 weeks with use of ILTA, but >10% of patients dropped out of the study due to pain (Tan et al 2002). Current methods for pain mitigation include small gauge needles, cold sprays, distraction, and topical anesthetics, each with their own limitations (Want et al. 2012). Controlling pain is important as it can result in several physiological, psychological, and emotional consequences such as hypoxemia, vasovagal reaction, tachycardia, life-long needle phobia, fear of other procedures, higher levels of pain during other procedures, and possible avoidance of the healthcare system as adults (Ballard et al 2018; Birnie et al 2018). Given limited treatment options for pediatric patients with AA, ameliorating the fear and pain associated with needle-based ILTA is preferable, and the Med-Jet injector may be a device that can do just that. If well-tolerated, well-designed, randomized clinical trials may be feasible in the pediatric population.

The Med-Jet-MBX needle-free injector (Med-Jet) is a novel, needle-free drug-delivery system, which we believe may be a solution to the pain and fear associated with needles. It uses regulated compressed air as a power source to accelerate an injectable fluid through a 0.005" orifice (6x smaller than a 30G needle) to penetrate the skin and deliver medication to a specific anatomical region (MedJet) The drug-delivery device is highly configurable allowing adjustable depth and volume parameters (MedJet). In addition, the high-performance design allows for triggering multiple injection sites rapidly which is practical when needing to treat large surface areas (MedJet).

## **Inclusion and Exclusion Criteria**

	Inclusion Criteria					
	Subjects must meet all of the following criteria to be eligible for this study:	Yes	No			
1	6-17 years of age.					
2	Diagnosed with alopecia areata by either: • A board-certified dermatologist, OR • Dermatology Nurse Practitioner, OR • Skin punch biopsy					
3	
 
Patient has at least 2 alopecic patches each measuring at least 2 cm^2 and are
 
Located on contralateral body sites OR
 
Within the same body site but separated by ≥ 1 cm
 
					
4	Patient is a candidate for intralesional triamcinolone.					
4	Patient able to give informed assent under IRB approval procedures when appropriate.					
5	At least one parent or guardian is able to provide informed consent.					

	Exclusion Criteria				
	A patient who meets any of the following criteria will be excluded from the study.	Yes	No		
1	Patient has alopecia totalis, alopecia universalis, or alopecia areata with ophiasis pattern.				
2	Known allergy or hypersensitivity to triamcinolone acetonide				
3	Pregnant, breastfeeding, or planning to get pregnant 4 weeks before, during, and 4 weeks after the study.				
4	Patient is unable/unwilling to provide informed assent when applicable.				
5	Known medical diagnosis or use of a medication that alters pain response at time of injection.				
6	Active infection at site designated for injection.				
7	If currently being treated for alopecia areata, the current treatment regimen has been started within less than 4 weeks of screening.				

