## • Study Visits

There will be four (4) or five (5) visits necessary for study participation:

- If all inclusion criteria are met and no exclusion criteria are met on the same day and the patient and their guardian wish to start the study, the baseline visit and screening visit can be completed on the same day. This will decrease the number of visits from 5 to 4. o
- If the patient has complete hair growth prior to the end of the study, they will complete all remaining visits, but they will not receive injections.
- Visit 1 Screening (within 5 weeks prior to baseline visit or same day, estimated time 1 hour if baseline activities are not performed):
  - We will obtain informed consent, review inclusion/exclusion criteria, obtain medical history (medical conditions, surgeries, alopecia areata history, medications, allergies, social history, and relevant family history), obtain vitals, perform a complete skin exam, efficacy assessments, patientreported pain assessments, and quality of life assessments. A urine pregnancy test will be performed for persons of childbearing potential.
- Visit 2 Baseline (Week 0, estimated time 1.5 hours if not performed the same day as screening):
  - This will be the in-office intervention visit to be scheduled within 4-6 weeks of screening visit. We will review inclusion/exclusion criteria, obtain concomitant medications, adverse events (AE), obtain vitals, perform limited skin examination with efficacy assessment, photograph of target lesions, perform intervention injections per protocol, collect patientreported pain assessments and quality of life assessments. A urine pregnancy test will be performed for persons of childbearing potential.
- Visits 3-5 Follow up study period (Week 4, 8, and 12, estimated time 30 minutes each):
  - A limited skin exam, photographs, review of AEs and concomitant medications, efficacy assessments, QoL assessments and pain assessments will be performed. ILTA will be administered at each visit unless complete regrowth has occurred. A urine pregnancy test will be performed for persons of childbearing potential.

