## **Prior and Concomitant Medications and Therapies**

All medications and therapies being taken/used by the subject at the time of consent or at any time during the study will be recorded. All medications and therapies for alopecia areata, will be recorded. The stop dates and reason for stopping all medications and therapies prohibited in the study will be recorded.

- Intervention
  - At least two patches; each measuring 2 cm2 and at least 1 cm from one another will be identified, mapped out, and photographed.
  - Only one of the alopecic patches will be treated.
  - The concentration of ILTA will be controlled at up to 1 mg per cubic centimeter (0.1 ml
     @ a maximum concentration of 10mg/ml) injected every 1 cm until patch has been fully treated. The researcher providing treatment will be properly trained to deliver intradermal injections using the syringe and needle-free system.
  - Med-Jet with Triamcinolone (TAC) Procedure ILTA will be administered into the patches. The PI and co-investigators will be performing interventions and follow proper training by the manufacturer on operation and handling of the device. Training will consist of a live course with a designated manufacturer technician supplemented with training videos. A standard sterile disposable 5 ml syringe will be used to draw TAC using standard sterile protocol. This syringe will be attached to the Med-Jet along with a sterile barrel and disposable sterile tip. The target lesion will be wiped with alcohol and injected with up to 10mg/ml of TAC directed towards the dermis to create a blanching wheal that is 1 cubic centimeter (total of 0.1 ml of injected fluid). The optimal injection pressure used on the subject will start at 130 pounds per square inch (psi) and increased by 5 psi until a blanching wheal is observed. The optimal pressure until the targeted patch is completely treated.
  - Patients will be treated at each visit unless complete regrowth has occurred.
     Photographs will be taken at each visit and activities will be completed as above.

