#### **Clinical Assessments**

- Physician Efficacy Assessments
  - Severity of Alopecia Tool (SALT) Score The SALT score is a visual tool to help assess percentage of hair loss on the scalp. The scalp is divided into four sections top, back, right side, and left side. Each section contributes to a total of 100% (i.e. top = 40%, back = 24%, sides = 18% each). Raters assess total percentage of hair loss in the section and then multiple is by the respective multiplier which is based on that sections total percentage of the scalp 40%, 24%, or 18%. Only terminal hairs are considered hair growth in this tool. (Olsen et al. 2004) Figure 1 illustrates the visual aid and allows for intuitive use. This is a static tool and only quantifies the hair loss at one point in time.
  - Alopecia Areata Investigator Global Assessment (AA-IGA) The AA-IGA categorizes the scalp hair loss into 5 categories based on the SALT score. The five categories are: 1 = None, 2 = Limited, 3 = Moderate, 4 = Severe, and 5 = Very Severe. The corresponding SALT scores for each category are: 1 = 0%, 2 = 1-20%, 3 = 21-49%, 4 = 50-94%, and 5 = > 95%. This is a static tool and only quantifies the hair loss at one point in time (Olsen 2004).
  - "Rule of Thumb" Assessment and Regrowth Categorization A patient's thumbprint projection is approximately 1% of the scalp surface area (King 2019). When selecting the alopecic patch for treatment and its comparator, thumb projections will be used to quantify the percentage of total scalp hair loss contributed by each these patches at baseline. At each subsequent visit, the thumbprint projection from baseline will be used to determine percent of regrowth since baseline. Based on regrowth, the patient will be categorized into one of 6 categories: A0-5. Where A0 = no change or further loss, A1 = 1-24% regrowth, A2 = 25-49% regrowth, A3 = 50-74% regrowth, A4 = 75-99% regrowth, and A5 = 100% regrowth.
- Patient-Reported Efficacy Assessments
  - Patient-Reported Hair Loss Whole Scalp This assessment will apply to the subject's whole scalp surface area. This question will be asked at every visit. And it will include 5 numerical categories: 0 = No missing hair (0% of my scalp is missing hair; I have a full head of hair); 1 = limited area (1% to 20% of my scalp is missing hair); 2 = moderate area (21% to 49% of my scalp is missing hair); 3 = large area (50% to 94% of my scalp is missing hair); and 4 = Nearly all or all (95% to 100% of my scalp is missing hair).

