## **Drugs or Devices**

- Triamcinolone acetonide injection therapy
  - Triamcinolone acetonide is not being trialed in this study. It is only included here for informational purposes given its significant role in our study.
  - Mechanism of Action: Triamcinolone is an organic lipophilic compound under the class of glucocorticoids which has a vast role in treatment of inflammatory skin conditions. It is proposed that TAC binds to glucocorticoid receptors in the cytoplasm and undergoes conformational changes. This drug-protein complex directly binds to DNA affecting gene regulation and transcription of various specific messenger ribonucleic acid (mRNA). In the skin, this leads to reduction of proinflammatory cytokines, t-cell lymphocytes, and suppression of keratinocyte growth factors. This is particularly helpful in psoriasis as cytokine/t-cell dysregulation and keratinocyte hyperproliferation is the pathogenic hallmark. In the dermis, glucocorticoids suppress fibroblasts activity and collagen/elastic fiber production which can lead to dermal volume reduction and subsequent dermal atrophy seen clinically.13
  - Dosing, Formulation, Frequency: Multiple formulations of triamcinolone acetonide exist including lotions, topical spray, nasal spray, cream, ointment, dental paste, and injectable suspension. The injectable suspensions are produced in two concentrations, 10mg/ml or 40mg/ml. In our study we will be performing injections using the 10mg/ml injectable suspension to inject up to 1 mg of TAC per cubic centimeter to minimize drug-related adverse events. The TAC may be diluted with sterile saline to a concentration less than 10 mg/ml. After one intervention of TAC, the first signs of involution start 4-14 days after injection with max involution at 2-3 months, followed by relapse at 6-12 months at which a repeat intervention may be considered.14
- Med-Jet Injector

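### Recent or ongoing treatment of the two study patches is neither excluded nor held stable, and no paired analysis is planned, so regrowth cannot be reliably attributed to the needle-free injections

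*Combined protocol and SAP*

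**What the plan says.** **Eligibility.** Exclusion 7 (Inclusion and Exclusion Criteria) is the only criterion on background alopecia treatment: "If currently being treated for alopecia areata, the current treatment regimen has been started within less than 4 weeks of screening". It names no class of treatment and sets no washout. An inclusion criterion reads "Patient is a candidate for intralesional triamcinolone", and no criterion deals with earlier or current needle ILTA.

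**Follow-up.** Prior and Concomitant Medications and Therapies says "All medications and therapies for alopecia areata, will be recorded" and "The stop dates and reason for stopping all medications and therapies prohibited in the study will be recorded". No section lists a prohibited therapy, requires a regimen to stay stable, or says how data after a change are handled. The Study Timeline collects concomitant medications at baseline and at Weeks 4, 8 and 12. No patch-level record of them is described.

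**Control.** The intervention text says "Only one of the alopecic patches will be treated". Clinical Assessments adds "When selecting the alopecic patch for treatment and its comparator, thumb projections will be used", and later regrowth is graded A0 to A5 against baseline. SALT, AA-IGA and patient-reported hair loss describe the whole scalp.

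**Analysis.** The Data Analysis Plan names AUROC, the chi-square test, the Mann-Whitney test and a cutoff of 0.05. It has no paired method and no adjustment for background therapy.

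**Timing.** Study Visits lets screening fall on the day of baseline or up to 5 weeks before it, yet also describes the baseline visit as "to be scheduled within 4-6 weeks of screening visit". The Study Timeline shows Week -4 to 0. Drugs or Devices gives the time course of one triamcinolone injection: "the first signs of involution start 4-14 days after injection with max involution at 2-3 months".

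**The concern.** Efficacy is a secondary objective, and it rests on regrowth after baseline and on a comparator patch taken to be untreated. A child several weeks into needle ILTA is eligible under exclusion 7. A child who has recently stopped may not count as currently treated and could enter with no washout. If that treatment reached only one of the two patches, it enters the patch contrast directly. On the treated patch it is credited to the device; on the comparator it hides a device effect. For whole-scalp measures any active background therapy adds to the observed change, and only one patch is injected. If exposure is not recorded by patch as the study runs, it may not be recoverable later.

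**Working it through.** **Figure to reproduce.** The plan states no efficacy target, response rate or power. Its 15 subjects are justified by pilot status and earlier pain scores, and the argument below does not depend on how 15 was reached.

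**1. Timing, from the document's own numbers.** Two to three months is 2 × 52/12 = 8.7 to 3 × 52/12 = 13 weeks. Take an ILTA injection given 4 weeks before screening, the shortest interval allowed for a current regimen, with a gap of *g* weeks from screening to baseline. Its maximum falls at study week 8.7 − (4 + *g*) to 13 − (4 + *g*).

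| Gap *g* (weeks) | Injection to baseline (weeks) | Maximum at study week |
|---|---|---|
| 0 | 4 | 4.7 to 9 |
| 4 | 8 | 0.7 to 5 |
| 5 | 9 | −0.3 to 4 |
| 6 | 10 | −1.3 to 3 |

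Every row overlaps the 12-week follow-up. Because the rule counts to screening, the interval to the first study injection can be anything from 4 to 10 weeks at the limit of the rule.

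**2. Treated patch alone.** At 10 of 15 responders the exact 95% interval is 38% to 88%. With no device effect and a background response *q* of 0.20 to 0.65, the treated patch would still show 15 × 0.20 = 3.0 to 15 × 0.65 = 9.8 expected responders. The value 0.65 is borrowed from the chart review cited in Background (more than 50% improvement in 65% of children at 12 weeks). The other rates are assumptions.

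**3. Paired contrast, background equal in both patches.** Assume 15 pairs, independent patches and an exact two-sided McNemar test at 0.05, counting rejections in favour of the treated patch. With device effect *d*, the treated-patch response is *t* = 1 − (1 − *q*)(1 − *d*). The discordant probabilities are *t*(1 − *q*) and *q*(1 − *t*). For *q* = 0.20 and *d* = 0.65: *t* = 1 − 0.80 × 0.35 = 0.72, and the difference is 0.72 − 0.20 = 0.52.

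| *q* | False positive, *d* = 0 | Difference, *d* = 0.65 | Power, *d* = 0.65 |
|---|---|---|---|
| 0 | 0% | 0.65 | 99% |
| 0.20 | 0.4% | 0.52 | 71% |
| 0.35 | 0.8% | 0.42 | 48% |
| 0.50 | 0.9% | 0.33 | 29% |
| 0.65 | 0.8% | 0.23 | 13% |

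Equal background therefore creates no false effect in a paired analysis, but it costs power.

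**4. Paired contrast, background on one patch.** With no device effect, 0.65 in a treated patch carrying background ILTA and 0.20 in the comparator, the false difference is 0.65 − 0.20 = 0.45. The test favours the treated patch 55% of the time. This puts all 15 children in that position. If a fraction *f* are exposed, the expected false difference is 0.45 × *f*: one child in 15 gives 0.03, five in 15 give 0.15. In the other direction, if the device brings the treated patch to 0.65 and background ILTA brings the comparator to 0.65, the expected difference is 0 instead of 0.45.

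**The case against.** The strongest reply is that each child has an untreated comparator patch, so regrowth can be attributed. For systemic or scalp-wide therapy and for spontaneous regrowth this largely stands, as step 3 shows, provided the patches are compared as pairs. The plan does not provide for that comparison, whole-scalp measures cannot use it, and it does not remove patch-specific treatment.

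A reader might infer that regrowth cannot be attributed at all, or that any therapy may be added during the study. The documents do not support either. They have a comparator, they record all alopecia therapies, and the reference to prohibited therapies implies that some restriction was meant. No text says that background ILTA may go into a study patch, and the statement that only one patch is treated can be read as ruling it out for the comparator. What stands is an omission: no rule addresses it, and the list is missing.

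A child two weeks after a needle injection might reasonably be regarded as currently treated, since the study itself injects every 4 weeks. The wording leaves that to the investigator.

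The 2-3 months figure comes from general drug text about involution, in which psoriasis is the disease named. It is not specific to hair and says nothing about topical or systemic regimens. It is, however, the only time course the protocol gives for triamcinolone, and the Background also uses 12 weeks for ILTA response.

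Finally, allowing established background therapy is a defensible choice in a 15-child pilot whose primary aim is tolerability. That argues for modest weight, not for leaving the gap.

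**Conclusion.** The point holds in limited form: under the plan as written, regrowth cannot be reliably attributed to the needle-free injections. The weakness is greatest for patch-specific background treatment, for whole-scalp measures and for any analysis of the treated patch alone. It is slight for scalp-wide therapy in a paired contrast, where the false-positive chance stays below 1% and the cost is power. Bias can go either way.

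The 55% false-positive figure is an upper illustration. It assumes that every child is exposed on the treated patch only, that patches respond independently, and that response is 0.65 against 0.20. The documents do not say how many children would be on or just off ILTA, so any count is an assumption. The Background notes that fear and pain often limit its use in children.

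A reader might extend the point to the pain results. Nothing here shows an effect on the primary tolerability objective. This is a change the sponsor should make, not one on which the trial stands or falls.

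**What to change.** 1. Amend exclusion 7 so that it counts to the first study injection and covers ongoing or recently stopped local treatment of either selected patch. The sponsor should choose the interval and justify it against the time course in Drugs or Devices.
2. Reconcile the reference to prohibited therapies with an actual list, or delete the term. Reconcile the three statements of the screening-to-baseline interval in Study Visits and the Study Timeline.
3. At each visit, record for each of the two patches any non-study alopecia treatment and any start, stop or change of regimen. Record the A0-A5 category separately for each patch, because the current text assigns it to the patient.
4. Make a paired treated-versus-comparator comparison of A0-A5, for example a Wilcoxon signed-rank test on all data, the main efficacy analysis.
5. Show the result without pairs exposed to non-study local treatment or a regimen change as a sensitivity analysis only. Such changes occur after baseline and probably follow poor regrowth, so dropping those pairs from the main analysis risks selection bias in a sample of 15.

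The cost is protocol wording, one case report form item per patch, one extra analysis and a slightly smaller pool of eligible children. The documents give no figure for the last of these. Patch-level recording needs to be in place before enrolment.

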## **Number of Research Participants**

This is a proof-of-concept pilot study. Collins et al. stated that the boundary between mild and moderate pain is a numerical rating scale (NRS) score of 3 (Collins 1997). Previous use of needle-free delivery methods have demonstrated an NRS < 3 (Nantel-Batista 2017, Vadeboncoeur 2017). Based on previous studies and the pilot nature of this study, 15 subjects will be enrolled to determine whether mild or moderate pain would be anticipated in future large scale assessments.

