## Pain Score Assessment

 Subjects will rate their pain using the Wong-baker FACES scale (Garra 2010) and a numerical rating scale (NRS) before and after the procedure. The NRS score ranges from 0-10 where 0 is no pain and 10 is the worst pain imaginable (Williamson 2005).

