- Administering ILTA using the needle-free drug delivery system will have a similar safety profile to conventional syringes with some additional benefits. One benefit of a needle-free system is the zero-risk of needle-stick injuries on providers. Lipoatrophy, a rare side effect of ILTA when injected too deep and in proximity to the subcutaneous fat, could be minimal with needle-free injections due to the operator-controlled injection depth parameter. Reported complications of needle-free injections were seen with devices using high driving pressures (1,420 psi); however, in this study, we will be using a low-pressure system (< 160 psi) (Seok 2016; Barolet 2018; Haneke 2012) This method of ILTA delivery has been used in the hyperhidrosis or nail psoriasis trials and none of the subjects encountered significant adverse effects with a low-pressure system (Vadeboncoeur 2017, Nantel-Battista 2014). This device is not currently approved for use in the United states by the FDA. We are requesting a determination from the IRB for investigational use of the Medjet as a nonsignificant risk medical device.

- The Medjet needle-less system propels an injectable fluid through a 0.005" orifice which is 6x smaller than a 30G needle (MedJet)> The small orifice combined with a quick delivery low-pressure system results in decreased pain scores for patients. In the nail psoriasis trial, 17 patients were injected over the proximal nail fold, which is a rather sensitive area, and reported a mean pain score of 2.1 based on a 10-point scale (Nantel-Battista 2017). Similar results were seen in the hyperhidrosis trial with scoring an average 3 on a 10-point scale over the palms (Vadeboncoeur 2017). Finally, the absence of a needle will create a more tolerable environment for patients who are needle phobic.

References

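### Fifteen subjects are said to determine whether pain is mild or moderate, but no SD, precision or decision rule supports this, and unless scores vary little the question will often stay open.

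*Combined protocol and SAP*

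**What the plan says.** The only justification of the sample size is under Number of Research Participants. It states that "the boundary between mild and moderate pain is a numerical rating scale (NRS) score of 3", adds that "Previous use of needle-free delivery methods have demonstrated an NRS < 3", and concludes that "15 subjects will be enrolled to determine whether mild or moderate pain would be anticipated in future large scale assessments". The stated grounds are earlier studies and the pilot nature of the trial.

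The earlier results appear under Drugs or Devices, in the part on the injector. In the nail psoriasis trial, 17 patients injected at the proximal nail fold "reported a mean pain score of 2.1 based on a 10-point scale". For the other trial the text reads: "Similar results were seen in the hyperhidrosis trial with scoring an average 3 on a 10-point scale over the palms".

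Under Pain Score Assessment, children rate pain before and after the procedure on the Wong-Baker FACES scale and on the NRS: "The NRS score ranges from 0-10 where 0 is no pain and 10 is the worst pain imaginable". The primary objective, under Objectives, is tolerability by patient-reported measures.

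The Data Analysis Plan names AUROC, the chi-square test and the Mann-Whitney test, with a 0.05 cutoff of unstated sidedness. It contains no one-sample test, confidence interval or threshold analysis of the pain score.

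**The concern.** The sample-size sentence credits 15 children with the ability to settle a two-way question about the primary outcome. Nothing in the protocol shows that they can. There is no SD from which to judge precision, no rule that turns data into a conclusion, and no planned analysis that uses the boundary.

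The cited results also leave little room. One prior mean is 0.9 points below the boundary and the other is on it. The second does not fit the sample-size section's own summary, which puts earlier results below 3.

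The Background presents good tolerability as the step that could make randomised paediatric trials feasible. A label of mild or moderate given without an interval could pass into the planning of those trials with more certainty than 15 children provide.

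There is also a difference of unit. The boundary is expressed as a score, while the earlier results are group means. A mean below 3 does not say how many children scored above 3.

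**Working it through.** **Inputs from the documents.** n = 15 and boundary 3 (Number of Research Participants); prior means 2.1 and 3 (Drugs or Devices); cutoff 0.05 (Data Analysis Plan).

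**Assumptions.** The documents give no SD, so a range of 1 to 3 points is used. Each child contributes one post-procedure NRS score. The two-sided 95% t interval is the main case, because sidedness is not stated.

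**The plan's own figure.** The 15 cannot be reproduced, because no calculation stands behind it. What can be checked is what 15 delivers.

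**Step 1: precision.** Half-width = t(0.975, 14) × SD / √15 = 2.145 × SD / 3.873 = 0.554 × SD.

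**Step 2: chance of a clear answer of mild.** The interval lies wholly below 3 when (3 − sample mean) / (s / √15) exceeds 2.145, where s is the sample SD. Under a true mean of 2.1 this ratio follows a non-central t distribution with 14 degrees of freedom and non-centrality (3 − 2.1) × √15 / SD = 3.486 / SD.

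| Assumed SD | Half-width (points) | Non-centrality | Chance that the interval is wholly below 3, true mean 2.1 |
|---|---|---|---|
| 1 | 0.55 | 3.49 | 90% |
| 1.5 | 0.83 | 2.32 | 58% |
| 2 | 1.11 | 1.74 | 37% |
| 2.5 | 1.38 | 1.39 | 25% |
| 3 | 1.66 | 1.16 | 19% |

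Solved for the SD, the chance reaches 80% only if the SD is about 1.16 or less, and 50% only if it is about 1.66 or less.

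**Step 3: the other cited mean.** At a true mean of 3 the non-centrality is 0, so the chance of an interval wholly below 3 is 2.5% at any sample size. A larger trial would not change this.

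**Step 4: sensitivity to sidedness.** With a one-sided 0.05 criterion, the chances at a true mean of 2.1 are 95%, 71%, 50%, 38% and 30% for SD 1, 1.5, 2, 2.5 and 3. The 80% point moves to an SD of about 1.33.

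**Step 5: group mean and individual children.** A made-up example: 12 children score 1 and 3 children score 6. The mean is (12 × 1 + 3 × 6) / 15 = 30 / 15 = 2.0, yet 3 of 15 (20%) are above 3. The exact (Clopper-Pearson) 95% interval for 3 of 15 is 4% to 48%.

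**Step 6: the two accounts of earlier results.** The sample-size section says that earlier needle-free use gave NRS below 3. The device section gives 2.1 and an average of 3. The first figure fits that summary and the second does not.

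**The case against.** The strongest reply is that this is a pilot, says so, and rests the 15 on that status. A pilot need not be powered, and the protocol claims no power. That stands, and it is why the point does not ask for more patients. It does not rescue the wording: a pilot can estimate, but the sentence says that it will determine.

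The second reply is that the result depends on an SD that the documents do not give. That also stands. At a true mean of 2.1 and an SD of 1, fifteen children give a clear answer nine times in ten. The finding is therefore conditional.

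Third, 2.1 and 3 are past results from nail folds and palms, and the palm study in the reference list used a different drug. A reader might take them as the means that the protocol expects for this trial. It does not say so. They are used here only because they are the sole pain means for needle-free injection that the documents supply.

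Two further inferences are tempting and unsupported:

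- A reader might infer that any mean just under 3 will be declared mild. No such rule is written; the gap is that there is no rule at all.
- A reader might shrink the sample because the Background reports that ">10% of patients dropped out of the study due to pain". That figure comes from a chart review of intralesional triamcinolone, cited in a discussion of fear and pain of injections, and is not a rate for this device. Since pain is rated from the first treatment visit, a child who leaves because of pain may already have given a score.

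**Conclusion.** The point holds in a limited form and should be fixed. The sample-size section claims that 15 subjects will determine whether pain is mild or moderate, with no SD, precision, decision rule or matching analysis behind the claim. Under an assumed SD of 1 to 3, the interval extends 0.55 to 1.66 points either side of the mean. The chance of an interval wholly below 3 runs from 90% down to 19% at a true mean of 2.1, and is 2.5% at a true mean of 3. Unless the SD is small and the true mean is near 2.1, fifteen children will often leave the question unresolved.

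A reader might go further and conclude that 15 is the wrong number or that the sample-size arithmetic is mistaken. The documents do not support that: they contain no calculation to be wrong, and a sample of 15 is defensible for estimation. The fault lies in what the number is said to deliver. The conflict between the two accounts of earlier results needs no assumption and stands as it is.

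**What to change.** Keep 15 and make four changes.

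1. Under Number of Research Participants, restate the aim along these lines: fifteen children will be enrolled to estimate mean post-procedure NRS with a 95% confidence interval, whose half-width is 0.55 SD, or about 1.1 points if the SD is 2.
2. In the Data Analysis Plan, add that interval and a three-way reading: mild if the whole interval is below 3, moderate if it is wholly above 3, and otherwise unresolved.
3. Beside the mean, report the number of children with NRS above 3 and its exact 95% interval; 3 of 15, for example, gives 4% to 48%.
4. Reconcile the statement that earlier results were below 3 with the average of 3 given under Drugs or Devices.

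The cost is a few sentences, with no extra patients, visits or procedures. The drawback for the sponsor is that the stated claim becomes less favourable and admits an inconclusive result.
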